
Nurse Care Managers, hired for the intervention, will have, at a minimum, a Bachelor of Science in Nursing. The PI will provide one week (40 hours) of PD care management education and training to the CHAPS Nurse Care Managers. These Care Managers will be monitored to confirm that care protocols, listed in the Care Manual, are being followed. Nurse Care Managers will also follow established nursing protocols per their site and as authorized by their nursing license. The PI will meet with Care Managers on a regular basis (weekly, then reduced to monthly when that reduction is made as a collaborative decision by the Nurse Care Managers and the PI). Meetings will provide the platform for consultation with the PI and for the Care Managers to share ideas about care management while maintaining patient confidentiality. These meetings will also support and monitor program implementation fidelity.

Because clinical cases and care management decisions are reviewed in these meetings, care delivery is monitored and proper care can be ensured. This approach mirrors, and in fact may surpass, the depth of supervision that is provided in usual care with “physician extenders” such as nurse practitioners, physician assistants, and specially trained nurses.

An analysis of CHAPS program costs and of the cost offset of VA healthcare utilization across the two arms will be conducted. Analyses of program implementation barriers and facilitators from veterans’ and from those involved in the intervention will also be conducted.

Research Design and Methods 2 –CHAPS Intervention Description

The intervention to be implemented and evaluated. The CHAPS intervention focuses on early identification of PD-specific problems and management of those problems. CHAPS tool and protocols include the following:

Assessment:

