Discussions of veteran medical information to outside community agencies will be conducted in an office with the door closed to maintain confidentiality. Medical information will be faxed to a secure fax that is accessible only to the recipient. SSNs will not be included in the transmission of medical information.

b) We will also use tracking capabilities within Microsoft Access to supplement the capabilities of CPRS. CPRS currently contains all progress notes, medications, laboratory, and radiology reports, but it doesn't contain some tools for facilitating care management of patients. Desired capabilities include the ability to quickly examine all upcoming tasks across a panel of patients, retrieve notes relevant to a specific problem area, or to schedule reminders to oneself. These capabilities reside within an Access relational database. For example, a care manager would click on a button for "active problems," then a list of problems would appear. If "excessive daytime sleepiness" is listed as a problem, then the care manager will be able to retrieve all historical actions that this person has taken relevant to this topic in the study. The care manager will view future scheduled actions such as, calling the subject in one week to assess if symptoms are worsening.

In addition, templates for the self-management care plan ("My Action Plan", *Appendix 4*) will be

programmed into the MS Access database. These care plans can be largely populated with data already collected in the assessment tools and other forms in Access. During telephone meetings with the subject, the nurse will enter data in to the patient's self management care plan, "My Action Plan" to summarize the clinical content of the encounter as well as to remind the subject about changes in lifestyle habits that should take place between encounters. These self-management care plans will be printed and given (mailed or in-person) to veteran subjects.

A summarized version of the Overall Care Plan "CHAPS Care Tracker" (Appendix 3) generated by Microsoft Access will be copied and pasted into CPRS. CPRS notes will document care given by the CHAPS clinical team to better coordinate care given by other VA providers.

We plan to establish a specific Hospital Admission Notification in CPRS, at each site, to alert the CHAPS Nurse Care Managers (NCM) when an intervention patient is admitted to a VA hospital. This will help NCMs improve care delivery.

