Development of guideline adherence measures for those measures not previously operationalized is following a process in which PD indicator or care goal is converted to review criteria, which are then operationalized through specific clinical variables and chart review questions.¹² Each observable measurement is being mapped to an action/activity performed in the intervention. For example, a veteran with PD who has been identified as experiencing symptomatic orthostatic hypotension, then the patient is to be instructed about salt intake and head elevation for this care goal to be categorized as adherent. As another example, if the patient is taking antihypertensive medications and has symptomatic orthostatic hypotension, then this medication should be decreased.

Table 4. Categories and examples of adherence for selected PD care quality process measures or indicators (excluding assessment process measures)	
Categories of 38 PD indicators	PD QUALITY GOAL ADHERENCE EXAMPLES
Communication, Education, & Continuity	
 • Should have a comprehensive care plan agreed between the individual, their family and/or caregivers and specialist and secondary providers.
Reporting	
 • All veterans should be assessed for abuse.
Diagnosing PD	
 • Diagnosis should be reviewed regularly & re-considered if atypical features develop.
Medication use	
 • Outpatient medical record should contain an up-to-date medication list.
Management of motor symptoms	
 • If receiving therapy with a dopaminergic agent, veteran should be assessed for motor complications at least every 6 months.
Management of non-motor complications	
 • If a veteran with PD is diagnosed with dementia, then an assessment of decision-making capacity should be conducted.
Non-pharmacological approaches/therapies	
 • All veterans with PD who have impairment of ADLs or in walking ability should be referred for physical therapy.
Palliative care	
 • Should have in outpatient chart: an advance directive, documentation of discussion about who would be surrogate decision maker or a search for surrogate, or indication that there is no identified surrogate.

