Medical Record Abstraction. Veteran-participant medical records will be abstracted from VA CPRS by experienced, nurse chart abstractors after training in use of the tool by the PI and [name]. Abstractors will be blinded to randomization assignment. This trial’s tool will be adapted from an electronic tool (programmed in Microsoft Access) previously developed by [name] et al, 2007 and that already includes many of this study’s care process (guideline) measures. Development of the revised electronic tool is underway in the current pilot study. Orientation and training in use of the data collection tool will be conducted with the nurse chart abstractors when this task is begun in Year 4. Written guides, variable definitions, and use of categories such as yes, no, unknown, not documented, date, etc. will be provided.⁵² We will assess agreement and identify any areas needing further clarification by having both nurse chart abstractors apply the tool to the first 10 medical records; if necessary, the tool may be further refined at this point. Both nurse chart abstractors will abstract 10% (N=40) of the records, identified by random selection (after the initial 10 records). The PI will be available for questions throughout the chart abstraction process and will meet with the abstractors at least monthly during this process or more often as needed. New information or changes will be communicated in writing and reviewed at these meetings, to ensure that both abstractors are aware of them.

Process Evaluation. This component of the evaluation will examine the delivery of the intervention, the quality of its implementation (fidelity) and the organizational context (policies, personnel, structures, and procedures) influencing implementation and effectiveness. Since this intervention is a paradigm shift from

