Health Services Utilization. Physician visits, emergency department visits, hospital admissions, nursing home admissions (distinct from respite care), home care services, and pharmacy data for the period 12 months preceding enrollment and during the 18 months (or 24 months for the first 204 enrollees) of the intervention will be collected from the VISN-22 Data Warehouse. The VISN-22 Data Warehouse contains detailed clinical data about Veterans Administration care (including hospitalizations, clinic visits, prescribed medications and demographics) for 5 hospitals and 28 community-based clinics within the VA Desert Pacific Healthcare Network. The database includes admissions to non-VA hospitals if the VA reimburses those hospitals for the care delivered. CHAPS investigators will prepare a query to the VISN-22 Data Warehouse in Year 4 for these data on study participants.

Missing-data, respondent dropout, interviewer bias.

Missing-data: Data collected from medical record abstraction and administrative records will be complete and will not contain missing data. All survey data is collected by immediate computer entry using a computer software program (Microsoft Infopath or Microsoft Access) that will be programmed to incorporate appropriate skip patterns and flag invalid entries as the RA administers the telephone survey. This computer based data collection will produce a clean dataset with minimal missing data and no out-of-range entries. Periodic data quality checks will be carried out by the data manager to identify systematic patterns of missingness that may occur during data collection.

Respondent dropout: In order to reduce dropout due to the participant being unreachable, we will collect multiple contact phone numbers at enrollment and implement tracking procedures for contact attempts by the study team as outlines in the human subjects section. A toll-free number will be available for participants to reach the research staff and flexible interview times will be offered to participants. If necessary, surveys can be completed over multiple contacts with the participants.

Interviewer bias: Study research assistants that conduct the telephone surveys, and the nurse abstractors who conduct the medical record abstractions will be blinded to the intervention status of participants.

Data Management and Quality Control. Research subject level data will be maintained in 3 separate files:

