- 1) A master file (Registry) containing participant names, contact information (address and telephone number), a unique subject ID, social security number, dates of consent, and dates of each evaluation survey completion and respective human subject payment information for survey completion. There will be a separate master file for each participating site for a total of 5 master files. The Project Manager, Research Assistants, and Principal Investigator (PI) will have access to all 5 master files. Nurse care managers will only have access to the master file that correlates with their respective site. Nurse abstractors will have access to identifiers (subject name and social security number) for accessing subjects' individual records in the VA Computerized Patient Record System (CPRS). Social security numbers will be obtained to process subject payment.
- 2) A file containing the unique subject IDs and survey data. The Project Manager, Research Assistants (RA), PI, Statistician, and Data Analyst will have access to the survey data.
- 3) A randomization file that includes the unique subject IDs and randomization status. These data will be maintained in a separate location from care management data that is being collected for clinical care purposes. The Project Manager, Research Assistant (not the Interviewer), PI, Statistician, and Data Analyst will have access to the randomization file.

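### The plan says chart abstractors are blinded, but its procedures do not protect that blinding for the chart-abstracted part of the primary outcome

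*Combined protocol and SAP*

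**What the plan says.** The section on Medical Record Abstraction (Research Design and Methods 6) states "Abstractors will be blinded to randomization assignment". The paragraph on interviewer bias repeats it as a control for bias: "the nurse abstractors who conduct the medical record abstractions will be blinded to the intervention status of participants". Neither place describes a procedure.

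Other sections describe what the abstractors see and whom they consult:

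- **Source.** "Veteran-participant medical records will be abstracted from VA CPRS by experienced, nurse chart abstractors" (Medical Record Abstraction).
- **Content of that source.** The CHAPS Intervention Description (Research Design and Methods 2) has a summary of the CHAPS Care Tracker pasted into CPRS, and adds that "CPRS notes will document care given by the CHAPS clinical team to better coordinate care given by other VA providers".
- **The PI's role in abstraction.** The PI helps train the abstractors and meets them at least monthly. "The PI will be available for questions throughout the chart abstraction process" (Medical Record Abstraction).
- **The PI's knowledge of arm.** The Overview of Study Design describes regular meetings of the PI with the care managers, and relies on them to monitor care: "Because clinical cases and care management decisions are reviewed in these meetings". Data Management and Quality Control lists the PI for the allocation file: "PI, Statistician, and Data Analyst will have access to the randomization file".

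**The concern.** Masked abstraction is the safeguard the plan offers for the chart part of its primary outcome. A chart that carries CHAPS documentation shows the arm to whoever reads it. A scoring question put to someone who knows intervention cases can be answered with the arm in mind, even unintentionally. If a borderline entry is then read more generously in one arm, the adherence difference shifts for a reason unrelated to care. A reader of the trial report would also take the statement of blinded abstraction at face value, although the design does not deliver it.

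A second issue concerns interpretation. The Primary Outcome section says "Each observable measurement is being mapped to an action/activity performed in the intervention". A CHAPS nurse's own note may therefore be the only evidence that an indicator was met, and the abstraction plan as described does not record who delivered the care. The result could not be split into care documented only by CHAPS and care given by other providers.

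**Working it through.** This point rests on the text, so the main check sets the sections side by side.

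**1. Does the chart reveal the arm?** Abstractors work in CPRS, with name and social security number for opening each chart (Data Management and Quality Control). CHAPS summaries and notes are in CPRS. Care management is given to the intervention arm only; the usual care arm continues the care it would otherwise have had. Care managers call at least monthly, unless the veteran asks for fewer calls, and reassess every 6 months, so CHAPS entries should recur over follow-up. The plan's own section on limitations accepts that physicians will learn which patients are in the intervention from CHAPS communications.

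**2. Is there a masking step?** The documents describe no removal or hiding of CHAPS entries before abstraction, no prepared extract, no masked person to answer scoring questions, and no check of whether blinding held. Research Design and Methods 7 refers to de-identified record data. That does not help, because removing a name does not remove a CHAPS note.

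**3. Is the PI independent of allocation?** The case-review meetings expose the PI to intervention patients. The randomization file is open to the PI under Data Management and Quality Control, whereas the section on randomization says the lists are accessible only to the Project Manager. These two statements must be reconciled. Even if the stricter one governs, the case-review meetings remain.

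**4. Would the quality checks detect a shared bias?** Both abstractors score the first 10 charts and a random 10% of the rest. This measures their agreement. Two abstractors who both see the CHAPS notes can agree and lean the same way.

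**5. Can the size be calculated?** No. It would need the standard deviation of the adherence score, the number of applicable indicators per patient, and a scoring shift. The documents give 38 indicators in total, some of them conditional, and none of these three quantities.

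What can be shown is how the planned test would respond to a shift that is simply assumed. The plan's Table 3 reproduces: a two-sided 5% two-sample t test with 90% power needs 235, 173 and 133 per arm for effects of 0.3, 0.35 and 0.4 SD. With 133 per arm the standard error of the standardised difference is √(2/133) = 0.1226. For a shift of b SD and no true effect, the rejection rate under a normal approximation is Φ(b/0.1226 − 1.96) + Φ(−b/0.1226 − 1.96).

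| Assumed shift b (SD) | b / 0.1226 | Rejection rate |
|---|---|---|
| 0 | 0 | 5% |
| 0.05 | 0.41 | 7% |
| 0.10 | 0.82 | 13% |
| 0.20 | 1.63 | 37% |

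The shifts are hypothetical and refer to the whole adherence score. They show why masking matters here. They do not estimate a bias in this trial.

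**The case against.** Several arguments on the other side are sound, and they set the limits of the point.

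- **The primary outcome is not only chart data.** It also uses the telephone survey, notably for education, counselling and referral, and the interviewer is stated to be blinded. A reader might infer that the whole primary outcome lacks masking. The documents support this only for the chart component.
- **Discretion is limited.** Indicators are turned into specific variables and chart review questions. There are written guides, variable definitions, fixed response categories and written notice of changes. These reduce the room for leniency but do not blind anyone.
- **The PI's role is modest as described.** The plan has the PI available for questions. It does not say that the PI decides scores, discusses identified patients or discloses allocation, and a second person shares the training. Even so, no one without access to allocation is assigned to answer scoring questions.
- **Nurse-delivered care is part of the intended effect.** A reader might infer that crediting a CHAPS note is bias in itself. It is not. The outcome measures care processes, the intervention is a nurse delivering them, and the theoretical framework names adherence as the mechanism. Denying credit for CHAPS-only care would remove part of the effect the trial is meant to measure.
- **Filtering CHAPS-titled notes would not restore blinding.** Since physicians receive CHAPS communications, other providers' notes may also reveal the arm. Filtering could also delete genuine evidence of adherence.

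**Conclusion.** The concern holds for the chart-abstracted component of the primary outcome. The plan claims blinded abstraction, but its procedures put arm-revealing entries in the abstractors' source and make a PI who knows intervention cases their point of reference. The claim is unprotected as written; the documents do not establish that blinding would be impossible under every arrangement.

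No size can be attached. A reader might assume a count of applicable indicators and a standard deviation, and conclude that a large share of the planned 0.4 SD effect could be artefact. The documents supply neither input, and such a figure would mix lenient scoring with care that was really given. Nor do they show that any bias occurs.

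The conclusion assumes that CHAPS notes are entered as described and that no masking procedure exists outside these documents.

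**What to change.** 1. **Withdraw the statement that abstractors are blinded**, in both places, and report chart abstraction as unmasked. Keep the separate statement about the survey interviewer.
2. **Re-route scoring questions.** Send them, without patient identity or arm, to an existing team member who has no access to allocation and does not attend care-manager meetings. Issue each ruling in writing and apply it to all charts. The co-investigators are not on the stated access list for the randomization file, but the documents do not settle who attends the meetings, so the sponsor must name a person who meets both conditions. Reconcile the two statements on access to the allocation lists at the same time.
3. **Add a source field for each met chart indicator** (CHAPS note only, or other provider). Pre-specify a supportive breakdown of adherence by source, shown beside the unchanged primary analysis. Describe it as separating care documented only by CHAPS from care by other providers, and not as a bias-corrected estimate.

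The cost is one field in the abstraction tool, a reassigned query role and one additional analysis. The latest schedule places abstraction from May 2016 to April 2017 and the document is dated 12/5/2016, so the field may have to be back-filled in charts already abstracted. The sponsor also accepts a less favourable masking statement.
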